10.0 STUDY PROCEDURES

10.1 Methods: After enrollment as above, co-investigators of this study or the assigned coordinator will be doing the consent. Patient will be randomized to intervention and control arms in a 2:1 ratio. The intervention arm will receive a dedicated workshop for one and a half hours every 2 weeks. We aim to start a 6 month long program with weekly creative writings workshops, and patient enrollment in the study will continue through the 1st 4.5 months of the 6 month period so that the last enrolled patient could complete 2 classes per month for two months. Each patient will be asked to attend at least two classes per month for a total of two months. These workshops will be held at Hershey Medical Center (HMC). At the initiation of the study along with consent we will collect baseline scores in both groups for each parameter as below. Somatic Symptom Burden (SSM-8 - Figure 2 - reference section), depression symptoms using PHQ-9 (Figure 3 – reference section), and anxiety symptoms using GAD-7 (Figure 4 – reference section) will be collected monthly and following intervention completion.

We will collect mood scores pre and post each session. We will use Emotional Thermometer Scale (EMS) from [name] (Feb. 2010), diagram for scales is shown in figure 1. Please see supplementary index for a letter of permission to use from [name]. We will give the Thermometer scales and collect scores pre and post each session and also collect scores pre and post completion of entire course. Control group will do EMS on monthly basis along with other parameters. At the end of the study we will review all participants' medical charts to count view the number of emergency room visits and hospitalizations each participant experienced during the study period. These will be further broken down in categories based on cancer

Institutional Review Board

related vs non-cancer related visits. We will also review their most current cancer disease status after completion of the workshops and categorize whether their status is considered to be stable, progressing, or in remission. Both groups will also receive follow up mood and symptom surveys twice a month for up to 2 months after completion of the participant's two to three month study period.

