The control arm will receive a book (i.e., *Writing Down Bones* by Natalie Goldberg) on creative writing and asked to read and do writing activities for one and a half hours once every two weeks. At the completion of the two-month participation or completion of 4 sessions control patients will be given the opportunity to enroll in the creative writing workshops for the remainder of the study period of 6 months. We will collect scores from control arm through the same Emotion Thermometers Scale on a monthly basis. Pre-intervention scores will be obtained at the time of consent or one week prior to the planned start of session 1 for workshop (either in the clinic if possible or mail the score sheet to patients with an enclosed stamped envelope for return of the scales). Depending on participant preference, we can send them emails of the REDCAP surveys containing the same information at set intervals. A sample of the REDCAP surveys is included in supplementary materials. We will also send participants in the control arm a stamped return envelope on a monthly basis if not able to get score sheets in a clinic or over REDCAP, depending on patient convenience and preference. We will call the participants once every 3-4 weeks to check in on their progress. Please see a calendar at the end for details.

To assess for possible confounding results of patients participating in the concurrent exercise study, we will ask participants if they are also enrolled in the exercise study at enrollment and perform a subset analysis for patients who are in the exercise study. They will be randomized into either control or intervention group in the same manner as the other patients in the study. We will additionally include a section of the survey to ask about regular exercise (more than 30 minutes, three times a week) and do a subset analysis of these patients as well.

We will be collaborating with the Department of psychiatry at HMC - [name], [name], and [name]. Any subject who requests psychiatry follow up will be referred to [name]. If participants report the presence of suicidal ideation per question nine on the PHQ-9 [i.e., Thoughts that you would be better off dead or of hurting yourself in some way], they will be referred on an urgent basis to [name] or [name]. In the event [name] and/or [name] are unavailable for follow-up, If any active suicidal thoughts are reported, participants will be referred directly to Emergency Department at Hershey Medical Center.

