22.0 TABLES and FIGURES for the STUDY**Table 1: DEMOGRAPHICS**

Participant	1	2	3	4	5	6	7...
Serial Number							
Alphanumeric code							
Medical Record Number							
Gender							
Age							
Living Alone vs with family/caretaker							
Primary Cancer Type							
Cancer Stage							
ECOG Performance Status							
Enrolled in the Exercise Study							
Regular exercise on or off the exercise study- >30mins three times a week							
Current Treatment (Surgery, Radiation, Chemo)							
Disease status at completion of study (Stable, Progression, Remission)							
Psychiatric history (previous diagnoses or hospitalizations)							
Current Psychiatric Medications							

Figure 1: Emotion Thermometer Score (ETS)

Emotion Thermometers 5 items+help

Instructions: In the first four columns, please mark the number (0-10) that best describes how much emotional upset you have been experiencing in the past week, including today. In the last column please indicate how much you need help for these concerns.

1. Distress	2. Anxiety	3. Depression	4. Anger	5. Need Help
 An orange thermometer with a scale from 0 to 10. The bulb at the bottom is orange and the stem is orange. The top of the stem has three orange radiating lines. The number 10 is at the top and 0 is at the bottom.	 A green thermometer with a scale from 0 to 10. The bulb at the bottom is green and the stem is green. The top of the stem has three green radiating lines. The number 10 is at the top and 0 is at the bottom.	 A blue thermometer with a scale from 0 to 10. The bulb at the bottom is blue and the stem is blue. The top of the stem has three blue radiating lines. The number 10 is at the top and 0 is at the bottom.	 A red thermometer with a scale from 0 to 10. The bulb at the bottom is red and the stem is red. The top of the stem has three red radiating lines. The number 10 is at the top and 0 is at the bottom.	 A grey thermometer with a scale from 0 to 10. The bulb at the bottom is grey and the stem is grey. The top of the stem has three grey radiating lines. The number 10 is at the top and 0 is at the bottom.
Extreme				Desperately
None				Can manage by myself

Are you already getting help for these problems? N/A No Yes Do you want further help for these problems? No Yes

Alex J Mitchell © 2013

Figure 2: Somatic Symptom Scale

Somatic Symptom Scale – 8 (SSS-8)

During the past 7 days , how much have you been bothered by any of the following problems?					

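### During treatment the Emotion Thermometer is tied to the class in the workshop arm and to a clinic, REDCap or the post in the control arm, so a difference in setting can be counted as a workshop effect

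*Combined protocol and SAP*

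**What the plan says.** Section 9.4.1 makes thermometer mood scores, at baseline and after the intervention, a primary endpoint. PHQ-9 and GAD-7 severity is the other.

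Section 10.1 Methods sets out collection as follows.

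- **Baseline, both arms.** "Pre-intervention scores will be obtained at the time of consent or one week prior to the planned start of session 1 for workshop", and "either in the clinic if possible or mail the score sheet to patients". No difference between arms is given.
- **Thermometer, workshop arm.** "We will give the Thermometer scales and collect scores pre and post each session and also collect scores pre and post completion of entire course".
- **Thermometer, control arm.** "Control group will do EMS on monthly basis along with other parameters". The place is a clinic, REDCap or a stamped envelope, the envelope being sent "on a monthly basis if not able to get score sheets in a clinic or over REDCAP, depending on patient convenience and preference".
- **REDCap.** "Depending on participant preference, we can send them emails of the REDCAP surveys containing the same information at set intervals". This sentence is not limited to one arm.
- **PHQ-9, GAD-7 and SSS-8.** Monthly and after the intervention ends. No place or route is given for the workshop arm.
- **Follow-up after the study period.** Surveys go to both groups on one schedule.

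The thermometer form (Figure 1 in section 22.0) asks for the number that "best describes how much emotional upset you have been experiencing in the past week, including today".

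Section 11.1 plans a linear mixed model for within-group and between-group differences. It names no covariate, exclusion or sensitivity analysis for place or route, and it does not say which of the workshop arm's thermometer scores enter the comparison.

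**The concern.** Both arms start from a baseline taken in the same way. From then on the place of measurement follows the arm. A workshop patient's session scores come from a class, on a day that patient was able to attend. A control's scores come from a clinic visit, or from wherever the patient opens the email or envelope. The change from baseline therefore contains a change of setting that differs by arm.

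Randomisation does not remove this, because the difference arises after randomisation. Nor can the model: where setting and arm coincide, a setting term cannot be told apart from an arm term.

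The protocol gives two reasons to take a setting effect seriously. The form's window includes the day of completion. The pilot in section 5.2 reports scores lower after class than before it at each visit, so the score moves within one sitting. The outcome is also a self-report by patients who know which activity they were given. At stake is whether a significant thermometer difference can be read as an effect of the workshop.

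**Working it through.** **Inputs.** From 11.2: 40 and 20 patients, target 0.45 SD, at least 80% power, four time points, within-patient auto-correlation 0.2. From 11.1: significance level 0.05. Assumed: a two-sided test, and AR(1) correlation. The setting shift b is also assumed, at 0.1, 0.2 or 0.3 SD in favour of the workshop, because the documents give no figure for it. These shifts are 0.1/0.45 = 22%, 44% and 67% of the target effect.

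**Step 1: the plan's own figure.**

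- Variance of the mean of four AR(1) scores, in SD² units: [4 + 2(3×0.2 + 2×0.04 + 1×0.008)]/16 = 5.376/16 = 0.336.
- SE of the arm difference: √[0.336 × (1/40 + 1/20)] = √(0.336 × 0.075) = 0.1587.
- 0.45/0.1587 = 2.84. Two-sided power is 80.9% by the normal approximation and 79.6% by the noncentral t with 58 df.

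The stated 80% is reproduced. With equal correlation at all lags the variance is (1 + 3×0.2)/4 = 0.40 and power is 73.8% (normal), which does not match. AR(1) is therefore kept.

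**Step 2: false-positive rate with no workshop effect.** The rejection rate is P(|T| > 2.002), with T noncentral t on 58 df and noncentrality equal to the shift in the contrast divided by its SE. The plan does not say how baseline enters, so three cases are shown.

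(a) Mean of three later scores minus an unshifted baseline.

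- Variance of the mean of three: (3 + 4×0.2 + 2×0.04)/9 = 0.4311.
- Covariance with baseline: (0.2 + 0.04 + 0.008)/3 = 0.0827.
- Contrast variance: 1 + 0.4311 − 2×0.0827 = 1.2658. SE = √(1.2658 × 0.075) = 0.3081.
- Noncentrality: b/0.3081.

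(b) Mean of four scores, one of them an unshifted baseline. Noncentrality: 0.75b/0.1587.

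(c) Mean of four scores, all shifted. Noncentrality: b/0.1587.

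| Assumed shift b | (a) later minus baseline | (b) three of four shifted | (c) all four shifted |
|---|---|---|---|
| 0.1 SD | 6.2% | 7.5% | 9.5% |
| 0.2 SD | 9.8% | 15.3% | 23.6% |
| 0.3 SD | 16.0% | 28.6% | 46.0% |

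Case (c) is the ceiling. It does not fit a four-score average that includes the commonly collected baseline.

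**Step 3: controls who do not use the clinic.** The shift pictured here lies between a class day and a clinic day. If half the control forms were completed elsewhere and carried no shift (an assumption), a 0.2 SD shift averages 0.5 × 0.2 = 0.1 SD. The 0.1 row then applies: 6.2%, 7.5% and 9.5%.

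**The case against.** The case on the other side is substantial.

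- **Only the thermometer is tied to sessions.** A reader might infer that all primary scores are taken in class. The documents do not say so: for PHQ-9, GAD-7 and SSS-8 the workshop arm's place and route are left open. The thermometer score after the whole course, which is closest to the primary endpoint, has no stated place either. This stands.
- **Shared routes.** The REDCap sentence may cover both arms, and follow-up surveys go to both alike. This stands, but the session scores remain tied to the class.
- **Recall.** The thermometer looks back over a week, and PHQ-9 and GAD-7 over two weeks, which may dampen any effect of the day. This stands as a limit on size. The argument from the day of completion does not reach PHQ-9 or GAD-7.
- **The pilot.** A drop after class shows that the form moves within a sitting. It does not show that the place moves it, and a short-lived real benefit would look the same. This stands: the direction is plausible, not shown.
- **Clinic visits.** Section 10.1 says only a clinic. That these are treatment or results visits is an inference from recruitment in the cancer clinics.
- **Overlap.** If 11.1 chose scores taken away from sessions, most of the problem would go. True, but 11.1 makes no such choice, and a fixed choice of pre-class scores would still leave the arms measured in different places.
- **Material not shown.** Section 10.1 refers to a calendar, and 11.1 to a schema figure, neither of which can be read here. They may fix place and route. That does not undo the session-tied collection stated in 10.1.

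**Conclusion.** The point holds for the Emotion Thermometer scores collected during treatment. As written, the plan lets a primary self-report be measured in different settings by arm after a common baseline, and the planned model cannot separate the two. A setting difference can therefore be counted as a workshop effect. It would go too far to say that it will be, or that it must favour the workshop.

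On size, the 5% error rate becomes 6.2% to 9.5% for an assumed shift of 0.1 SD, 9.8% to 24% for 0.2 SD and 16% to 46% for 0.3 SD. The lower ends belong to a change from an unshifted baseline, which is nearest to the before-and-after wording of 9.4.1. The upper ends require every score in the comparison to be shifted, and all the figures fall if many control forms are completed outside a clinic. They rest on the assumed shifts, AR(1) correlation of 0.2, a two-sided test and complete data on 40 and 20 patients.

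For PHQ-9, GAD-7, SSS-8 and the end-of-course thermometer the finding is a gap in the text, not a demonstrated difference between arms. The matter should be settled before analysis, since it decides how a positive thermometer result can be read.

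**What to change.** In 10.1 and 11.1:

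1. State that the thermometer scores entering the between-arm comparison, including the end-of-course score, are collected in both arms by the same route (a REDCap link, or a mailed form for those without email), on the same fixed days counted from randomisation and not at a class.
2. Use pre-session and post-session scores only to describe the workshop arm.
3. Record the route and place of every form, and add a sensitivity analysis by route.
4. State the workshop arm's place and route for PHQ-9, GAD-7 and SSS-8. Move these scales to the common route only after the sponsor confirms that the existing referral process for PHQ-9 item 9 covers forms completed at home in both arms.
5. Bring the calendar and schema into line with this text.

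The cost is mainly wording, since the REDCap surveys and stamped envelopes are already planned. Return may be slightly lower than with collection in person; the calls planned every 3-4 weeks can serve as reminders. If PHQ-9 is moved too, posted forms are seen later than forms handed in, which is why step 4 waits for the sponsor's confirmation.

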11.0 Statistical Plan

11.1 Statistical Analysis Plan

Participants' basic demographic and baseline clinical measurements will be summarized using descriptive statistics. Those summarizations will be based on all patients as well as on patients within each group. This study has several main groups of outcome variables, which reflect several different domains of patient's mental health. The first group is the emotion thermometer (which has five sub-scales), the second is the somatic symptom scale (SSS-8), the third is the Patient Health Questionnaire (PHQ-9), and the fourth is the Generalized Anxiety Disorder questionnaire (GAD-7), which measures participants' anxiety. All the above outcome variable groups are based on questionnaires using Likert-scale questions to take the measurements, and each group may involve multiple sub-dimensions. Both the intervention group and the control group have repeated measures of the outcomes as shown in Figure 1. Graphical methods (such as the line plot of mean/SD values vs. time) will first be used to illustrate the mean and standard deviation values of the mode, depression, and anxiety scores through the time for both groups. These methods will help us detect the patterns of how the scores change over time (within-group change) and how the scores differ between groups. We will further use the linear mixed-effect model for repeated measures to analyze the within-group and between-group differences. Every sub-dimension will be analyzed individually, but we will also analyze the composite score for the dimensions. For the patients in the control group this study involves two stages (week 1-12 and week 13-20), and at the end of the 12th week, they can join the intervention group. This setting will allow us to study the effect of the intervention on the control group alone. For this part of analyses, linear mixed-effect models will be set up with the stage serves as an indicator variable in the model. The comparison of outcome variables between certain time points will also be done using paired tests. We will further investigate the possible factors that might affect the change of outcome variables over time. The factors are gender, race, marital status, time from cancer diagnosis (first 3 months, 3-6 months, more than 6 months) and cancer stages. This part of analyses will mainly be focused on the intervention group and the above factors will be examined in the linear mixed-effect models. All analyses will be performed using statistical software SAS version 9.4 or higher (SAS Institute, Cary, NC, USA) and the statistical significance level to be used is 0.05.

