
11.2 Sample size considerations:

We plan to enroll a total of 60 participants in the study – with 40 participants in the intervention group and 20 participants in the control group (2:1 ratio). This sample size is mainly determined by the capacity of the workshop. With this sample size we are able to detect a standard effect size (the mean difference measured in common standard deviation) of 0.45 with at least 80% statistical power (using two-sample repeated measure ANOVA model, assuming four time-points, and the within-patient auto-correlation being 0.2) .

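### The exercisers-only subset analyses in 10.1 cannot correct a chance imbalance in exercise-study enrolment; a baseline covariate in the all-patient model can, at almost no cost

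*Combined protocol and SAP*

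**What the plan says.** Section 10.1 gives the purpose as "To assess for possible confounding results of patients participating in the concurrent exercise study". Patients are asked at enrolment whether they are in that study, and the sponsor will "perform a subset analysis for patients who are in the exercise study". A survey section also asks about regular exercise (more than 30 minutes, three times a week), and the sponsor will "do a subset analysis of these patients as well". Co-enrolled patients are randomised in the same way as everyone else.

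No other use of the exercise data is described:

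- Section 9.2 stratifies randomisation by cancer type only.
- Section 11.1 lists gender, race, marital status, time from diagnosis and cancer stage as factors for the mixed models. Exercise is not among them, and that work is to focus mainly on the intervention group, so it does not adjust the between-arm contrast.
- Table 1 in section 22.0 has a row "Enrolled in the Exercise Study" and another for regular exercise on or off that study, so both variables are held for every participant.

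No expected number of co-enrolled patients is given, and no assumed effect of exercise on mood.

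**The concern.** The aim and the tool do not match. An arm comparison restricted to exercisers estimates the workshop effect in that group. If it differs from the overall estimate, the difference reflects effect modification or noise. If co-enrolment happens to be uneven between the 40 and the 20, the all-patient estimate carries the resulting shift whether or not the subset analysis is run. Analysing both strata and pooling them would be a form of adjustment, but the plan mentions exercisers only.

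At stake is a modest loss of precision in the main comparison, and a result from a handful of patients offered as the answer to a question it does not address.

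**Working it through.** **Inputs from the documents.** 40 versus 20 patients; a standardised effect "of 0.45 with at least 80% statistical power"; "assuming four time-points, and the within-patient auto-correlation being 0.2" (all section 11.2); "the statistical significance level to be used is 0.05" (section 11.1).

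**Assumptions.** Two-sided testing, AR(1) correlation, analysis of the mean of the four scores, no dropout, co-enrolment of 15%, 25% or 40% split 2:1, and an exercise effect of 0.25 to 0.5 SD arising after baseline.

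**Step 1: the plan's own power.** The variance of the mean of four scores, in units of the single-score variance, is

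[4 + 2(3×0.2 + 2×0.04 + 1×0.008)] / 16 = 5.376 / 16 = 0.336.

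The standard error of the arm contrast is √[0.336 × (1/40 + 1/20)] = √(0.336 × 0.075) = 0.159. Power for 0.45 is 80.9% by the normal approximation and 79.6% by the noncentral t, so the stated 80% is reproduced to within rounding of method. Under compound symmetry the variance factor is (1 + 3×0.2)/4 = 0.40 and power is 72.4% (noncentral t).

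**Step 2: the exerciser subset.** The same noncentral t calculation, with the subset's patients. The 95% half-width is t(0.975, n−2) × √[0.336 × (1/n1 + 1/n2)].

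| Share co-enrolled (assumed) | Patients | Power for 0.45, AR(1) | Power, compound symmetry | 95% half-width, AR(1) |
|---|---|---|---|---|
| 15% | 6 vs 3 | 15.9% | 14.1% | 0.97 SD |
| 25% | 10 vs 5 | 26.0% | 22.6% | 0.69 SD |
| 40% | 16 vs 8 | 40.3% | 34.9% | 0.52 SD |

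Every half-width exceeds the 0.45 target.

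**Step 3: how far chance imbalance moves the main estimate.** The SD of the arm difference in co-enrolment is √[p(1−p)(1/40 + 1/20)]. The shift is the imbalance times the exercise effect.

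| Share | Imbalance SD | 1-SD imbalance, effect 0.25 / 0.5 | 2-SD imbalance, effect 0.25 / 0.5 |
|---|---|---|---|
| 15% | 0.098 | 0.024 / 0.049 | 0.049 / 0.098 |
| 25% | 0.119 | 0.030 / 0.059 | 0.059 / 0.119 |
| 40% | 0.134 | 0.034 / 0.067 | 0.067 / 0.134 |

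A shift of a quarter of the target (0.45/4 = 0.1125 SD), in either direction, needs an imbalance of 0.1125/0.5 = 0.225 when the exercise effect is 0.5 SD. By the normal approximation its probability is about 2%, 6% or 9% at the three shares. With an effect of 0.25 SD the imbalance needed is 0.45, and the probability is below 0.1% at every share. Even the 2-SD shifts at 0.5 SD are only 0.098/0.159 = 0.6 to 0.134/0.159 = 0.8 standard errors.

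**Step 4: what the covariate does.** With balanced covariates and no prognostic gain counted, power on all 60 is 79.6% with one covariate and 79.6% with two. Simulations (6,000 runs per scenario, shares of 10% to 50%) compared models with and without the exercise indicator:

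- Exercise effect 0.5 SD: power 78–81% adjusted against 73–77% unadjusted. In the 2.5% of allocations with the greatest excess of exercisers in the intervention arm, the unadjusted estimate averaged 0.52–0.60 against a true 0.45, and the adjusted estimate 0.43–0.46.
- Exercise effect 0.25 SD: power 79–80% adjusted against 78–79% unadjusted, so the gain is about one point at most.
- Over all allocations, both estimates averaged about 0.45.

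**The case against.** The strongest reply is that this is a randomised trial. Exercise-study enrolment is asked at enrolment, so the arms can differ on it only by chance. The unadjusted estimate is then unbiased on average, and such variation is part of the ordinary randomisation error that the test already allows for. That stands, and it limits the point to chance imbalance and precision. With only 20 controls and no stratification on exercise, a reader might infer that an imbalance large enough to matter is likely. The documents do not support that: step 3 puts a quarter-of-target shift at 2% to 9%, and only with an assumed exercise effect larger than the 0.45 for which the trial is sized.

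Four further replies have some force:

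- **Before–after endpoints.** Section 9.4.1 compares scores before and after intervention. An exercise effect already present at baseline would partly drop out, so the shifts apply only to an effect arising after baseline.
- **Modest claims for the subset.** The plan says it will assess confounding, and attaches neither a power claim nor a decision rule to the subset. Low power alone is therefore a weak criticism. What remains is that the subset comparison does not address the stated aim.
- **Timing of the regular-exercise item.** A reader might take both exercise variables to be baseline data because both are in Table 1. Section 10.1 gives no timing for the regular-exercise item, and the same table holds disease status at study completion, so baseline timing is not established.
- **Why exercise.** The plan names no adjustment covariates for the between-arm contrast, not even the stratification factor, so choosing this one may look like preference. But exercise is the factor that the protocol itself names as a possible source of confounding.

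**Conclusion.** The point holds as a minor improvement. The exercisers-only analyses can describe the effect in that group but cannot correct a chance imbalance in the all-patient comparison. Their power for 0.45 SD is about 16% to 40% at assumed shares of 15% to 40%.

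The exposure is small: about 0.02 to 0.07 SD for a typical imbalance and 0.05 to 0.13 SD for an uncommon one. It rests on an assumed 0.25 to 0.5 SD exercise effect arising after baseline, two-sided testing, AR(1) correlation and no dropout. The documents supply neither the share co-enrolled nor the exercise effect. The main comparison is not biased for want of the adjustment; the case for change is that a better method is available for data the sponsor already plans to collect.

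**What to change.** In sections 10.1 and 11.1:

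1. Enter exercise-study enrolment, as recorded at enrolment, as a fixed covariate in the between-arm linear mixed model on all randomised patients.
2. State when the regular-exercise item is asked. Add it as a second covariate only if it is confirmed as asked before randomisation. Do not adjust for exercise reported afterwards, since the workshop may affect it.
3. Report the exercise-by-arm interaction as exploratory, and keep the subset estimates as descriptive.

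The cost is one degree of freedom, or two if regular exercise is added; calculated power stays at 79.6% either way. Exercise-study enrolment needs no new data collection. Regular exercise needs its timing fixed. The two variables overlap, because the Table 1 row counts regular exercise on or off the exercise study, so their separate coefficients should not be over-read.
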